6.6.1. Glasdegib

Glasdegib does not need to be delayed or dose reduced for hematologic toxicity deemed unrelated/unlikely related to glasdegib by the investigator.

Participants experiencing Grade 3 or 4 nonhematological toxicities potentially attributable to glasdegib should have their glasdegib treatment interrupted regardless of when it occurs in the cycle until the toxicity resolves or returns to baseline or \leq Grade 1, as described in [Table 2](#). If these parameters have not been met following >28 consecutive days of dose interruption, glasdegib should be permanently discontinued. If glasdegib treatment is permanently discontinued, participants may continue single agent treatment with azacitidine, if according to the investigator's judgment a clinical benefit has been observed, and following discussion between the investigator and the sponsor.

Appropriate follow-up assessments should be implemented until adequate recovery (toxicity resolves or returns to baseline) occurs.

Depending on when the adverse event resolved, treatment interruption may lead to the participant missing all subsequent planned doses of glasdegib within the cycle. If the AE leading to treatment interruption recovers within the same cycle, recommencement of dosing in that cycle is allowed. The need for a dose reduction at the time of treatment resumption should be based on the criteria outlined in [Table 2](#), unless specifically agreed otherwise following discussion between the investigator and the sponsor. If a dose reduction for glasdegib is applied in the same cycle, the participant may need to receive a new supply of drug. Glasdegib doses omitted for toxicity will not be replaced within that cycle (eg, cycles will not be prolonged beyond the 28 days to make up for any missed glasdegib doses during that cycle).

Glasdegib may be interrupted or permanently discontinued for any reason as per GCP. Glasdegib should be permanently discontinued if interruptions are for more than 28 consecutive days. In the event of glasdegib treatment interruption for reasons other than

treatment-related toxicity (eg, elective surgery) for a duration >28 days, the details of treatment resumption will be determined in consultation with the Sponsor.

Dose reduction of glasdegib by 1 or, if necessary, 2 dose levels (Table 1) will be allowed depending on the type and severity of toxicity encountered. **NOTE:** In the specific situations where clinical benefit is observed, glasdegib can be reduced below 50 mg QD upon discussion with the sponsor. All dose modifications/adjustments must be clearly documented in the participant's notes and eCRF.

Once the glasdegib dose has been reduced, all subsequent cycles should be administered at that dose level, unless further dose reduction is required. Dose re-escalation is not allowed. Deviations from any of the dose modifications must be discussed and agreed with the sponsor Medical Monitor.

Table 1. Available Dose Levels

Glasdegib (mg QD)
100
75
50
25 *

* **NOTE:** If clinical benefit is observed, glasdegib may be reduced below 50 mg QD following Sponsor approval.

Dose modifications for treatment-related- non-hematologic toxicities (excluding QTc prolongation, muscle spasms, and myalgia) are outlined in Table 2.

Table 2. Dose Modifications for Non Hematologic Toxicities (Excluding QTc Prolongation, Muscle Spasms, and Myalgia)

Toxicity (NCI CTCAE version 4.03)	Glasdegib
≥ Grade 3 toxicity (nausea, vomiting, and/or diarrhea must persist at ≥ Grade 3 (despite maximal appropriate medical therapy) to require dose modification).	Hold glasdegib until toxicity has recovered to baseline or ≤ Grade 1. First episode: Decrease by 1 dose level Second episode: Decrease by 1 dose level Third episode: Permanently discontinue
Potential drug induced liver injury/Hy's Law (as defined in Appendix 5).	Interrupt glasdegib dosing. If an alternative cause is found, restarting of glasdegib at the same dose may be considered.
Confirmed drug induced liver injury/Hy's Law (as defined in Appendix 5).	Glasdegib should be permanently discontinued.

Participants will be closely monitored for potential cardiovascular symptoms per standard of care. Appropriate monitoring should include clinical examinations, vital signs, routine ECGs, and AE monitoring. In case of QTcF prolongation, concomitant conditions such as electrolyte imbalances, hypoxia, or use of medications affecting the QT interval should be ruled out and/or corrected. In case of clinically significant toxicities, glasdegib administration should be interrupted and the dose reduced as indicated in Table 3.

Concomitant administration of glasdegib with strong/moderate CYP3A4/5 inhibitors ([Appendix 10](#) or [Appendix 11](#)) and drugs with known risk of TdP ([Appendix 12](#)) is not recommended due to the potential for drug-drug interaction to prolong the QTc interval. However, if it is medically necessary for participants to use these medications please refer to [Appendix 6](#) for monitoring procedures. Investigators must be aware of the QTcF prolonging potential of all medications that participants on study are taking, and should take appropriate action when clinically indicated. Given the potential for QTcF prolongation, the measurement and immediate correction of electrolyte abnormalities such as potassium and magnesium, and of other reversible causes of QTcF prolongation such as hypoxia, are especially important. In the event that the QTcF interval is prolonged beyond 480 msec (CTCAE v. 4.03 \geq Grade 2), Table 3 must be referenced and actioned. Additional ECG and cardiac consultation should be obtained if clinically indicated.

Table 3. Glasdegib Dose Modifications for mQTcF Prolongation

CTCAE v 4.03	Grade 1	Grade 2	Grade 3	Grade 4
ECG QTc interval prolonged*	450-480 msec	481-500 msec	\geq 501 msec on at least 2 separate ECGs	QTc \geq 501 msec or $>$ 60 msec change from baseline and TdP or polymorphic ventricular tachycardia or signs/symptoms of serious arrhythmia

*The severity of QTc prolongation assessment is to be determined by calculating a mean QT of 3 consecutive ECGs performed approximately 2 minutes (but no longer than 5 minutes) apart using the Frederica correction method (mQTcF).

**Please see [Section 8.3.9](#) for protocol specified SAE reporting requirement of Grade 3 or 4 mQTcF prolongation.

Category	Action	Grade			
		1	2	3	4
General management	Assess electrolyte levels and supplement as clinically indicated		X	X	X
	Review and adjust concomitant medications with known QTc interval-prolonging effects		X	X	X
ECG monitoring	Monitor ECGs at least weekly for 2 weeks following resolution of mQTcF prolongation to \leq 480 msec		X	X	X
Initial glasdegib action	Discontinue and do not rechallenge				X
	Interrupt treatment			X	
	Continue treatment at same dose	X	X		

Table 3. Glasdegib Dose Modifications for mQTcF Prolongation

Resume glasdegib dosing	If no prior glasdegib dose interruption related to QTcF prolongation has occurred, resume at a reduced dose of 75 mg once daily when mQTcF interval returns to within 30 msec of baseline or ≤ 480 msec			X	
	If 1 prior glasdegib dose interruption related to QTcF prolongation has occurred, resume at a reduced dose of 50 mg once daily when mQTcF interval returns to within 30 msec of baseline or ≤ 480 msec			X	
Discontinue glasdegib permanently	If 2 prior glasdegib dose interruptions related to QTcF prolongation have occurred			X	

Dose modifications for glasdegib in case of drug class related AEs are outlined in Table 4.

Table 4. Dose Modifications for Glasdegib in Case of Drug Class Related AEs

Muscle Spasms or Myalgia	Grade 1	Grade 2	Grade 3
Glasdegib	
Continue at same dose level.
 
Administer oral rehydration solutions containing electrolytes.^a
 
Consider other appropriate interventions (eg, anti-spasmodics) as per institutional guidelines.
 
Evaluate levels of: CK, Vit B6, Vit D, ferritin, transferrin and electrolytes (Na, K, Mg, Ca and P).^b
 
If CK is elevated, evaluate urine and serum myoglobin, CK isoenzymes, and serum creatinine.
	
Continue at same dose level.
 
Administer oral re-hydration salts containing electrolytes.^a
 
Consider other appropriate interventions (eg, anti-spasmodics) as per institutional guidelines.
 
Evaluate levels of: CK, Vit B6, Vit D, ferritin, transferrin and electrolytes (Na, K, Mg, Ca and P).^b
 
If CK is elevated, evaluate urine and serum myoglobin, CK isoenzymes, and serum creatinine.
 
If event persists, hold dose until resolution to Grade ≤ 1.
	
Hold dose.
 
Administer oral re-hydration salts containing electrolytes.^a
 
Consider other appropriate interventions (eg, anti-spasmodics) as per institutional guidelines.
 
Evaluate levels of: CK, Vit B6, Vit D, ferritin, transferrin and electrolytes (Na, K, Mg, Ca and P).^b
 
If CK is elevated, evaluate urine and serum myoglobin, CK isoenzymes, and serum creatinine.
 
Upon resolution to Grade ≤ 1, restart study treatment at next lower dose level.
 
If the event does not resolve within 3 weeks to Grade ≤ 1, at the discretion of the Investigator the dose may be restarted at the next lower

Table 4. Dose Modifications for Glasdegib in Case of Drug Class Related AEs

Muscle Spasms or Myalgia	Grade 1	Grade 2	Grade 3
		Upon resolution, restart at prior dose, or for prolonged muscle spasms, consider reducing dose by one dose level.	dose level or the participant may be permanently discontinued from study treatment.

a. Electrolyte replacement drinks should include Na, K, Mg, Ca and P. Consideration should be given to ensuring adequate hydration prior to bedtime, and whenever fluid intake is decreased for a prolonged duration.

b. Labs may be drawn between protocol visits.

In the event of alopecia or dysgeusia, investigator discretion should be applied with respect to dose interruption and/or dose reduction of glasdegib as preliminary analysis of available clinical data suggests that these events are not dose dependent.

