6.1.2. Dosing Regimen

- Azacitidine will be administered 75 mg/m²/day for 7 days every 28 days on Days 1-7 (± 3 days) per local label or per the IP Manual (or SPC). Azacitidine may be administered by SC injection or IV infusion. Alternate dosing schedules to administer the 7 doses to accommodate participant and treatment center availability are allowed. The starting dose regimen will be the same as the most recent regimen received on the B1371019 or B1371012 study.
- Glasdegib 50, 75 or 100 mg will be orally administered daily and continuously. The starting dose regimen will be the same as the most recent regimen received on the B1371012 or B1371019 study.

Dose modifications are discussed in [Section 6.6](#).

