6.6. Dose Modification

Every effort should be made to administer the study drug treatment according to the planned dose and schedule.

In the event of Grade 3 or Grade 4 non-hematologic, study-treatment-related toxicity, dosing may be delayed and/or dose reduced. The glasdegib dose should be reduced 1 dose level at a time, in increments of 25 mg (75 mg QD, 50 mg QD, in the form of 3 or 2 x 25 mg tablets respectively). Glasdegib does not need to be delayed or dose reduced for hematologic, study-treatment-related toxicity.

Glasdegib may be interrupted or permanently discontinued for any reason as per GCP. Glasdegib should be permanently discontinued if:

interruptions are for more than 28 consecutive days when not required by the protocol (ie, HSCT period).

Dose escalations will not be allowed following glasdegib/placebo dose reductions. Dose modifications may occur in 3 ways:

Within a cycle: Dosing interruption until adequate recovery followed by dose reduction (if required) of glasdegib during a given treatment cycle.

Between cycles: The next treatment cycle may be delayed if toxicity from the preceding cycle persists.

In the next cycle: Dose reduction may be required based on toxicities experienced in the previous cycle.

When chemotherapy is given, a Cycle is determined by chemotherapy administration schedule. A Cycle is 28 days, but will be extended if there are dose delays or modifications in the chemotherapy backbone.

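### Table 3's fixed resumption doses after Grade 3 mQTcF prolongation give no dose reduction to participants already lowered, for another reason, to 75 mg (first event) or 50 mg (first or second event)

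*Protocol*

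**What the plan says.** Table 3 in Protocol 6.6.1 has two resume rows for Grade 3 mQTcF prolongation (501 msec or more on at least two ECGs). With no earlier QTcF-related interruption the site is to "resume at a reduced dose of 75 mg once daily when mQTcF interval returns to within 30 msec of baseline" or 480 msec or less. With one earlier interruption it is to "resume at a reduced dose of 50 mg once daily when mQTcF interval returns to within 30 msec of baseline", with the same alternative threshold. With two, glasdegib stops for good.

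The text before the table states its purpose: "In case of clinically significant toxicities, glasdegib administration should be interrupted and the dose reduced as indicated in Table 3". For QTcF beyond 480 msec, 6.6.1 adds that "Table 3 must be referenced and actioned".

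Other provisions bear on the same decision:

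- Section 6.1.2 foresees lower doses, "Glasdegib 50, 75 or 100 mg will be orally administered daily and continuously", and starts each participant on the last regimen from the earlier study. Tables 2 and 4 lower the dose by one level for other toxicities.
- Section 6.6, on treatment-related Grade 3 or 4 non-hematologic toxicity, says "The glasdegib dose should be reduced 1 dose level at a time, in increments of 25 mg".
- Section 6.6 also says "Dose escalations will not be allowed following glasdegib/placebo dose reductions", and 6.6.1 says "Dose re-escalation is not allowed".
- Table 1 lists 100, 75, 50 and 25 mg. Going below 50 mg requires observed clinical benefit and Sponsor approval.

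**The concern.** Tables 2 and 4 step down from whatever dose the participant is taking. Table 3 instead names two absolute doses, which form a descending ladder only for someone who starts at 100 mg. A participant lowered to 75 mg for, say, Grade 3 muscle spasms who then has a first Grade 3 mQTcF event is told to resume at 75 mg, the dose on which the event occurred. The table calls that dose reduced, and for this participant it is not.

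What is at stake is the dose given after a Grade 3 QTcF event with a drug whose QTc potential the protocol acknowledges in 6.5.1. No estimate, test or summary in the SAP is affected.

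**Working it through.** **Inputs.** Table 3 resumption doses: 75 mg at a first event and 50 mg at a second (6.6.1). Dose levels: 100, 75, 50 and 25 mg (Table 1). Possible doses on entry: 50, 75 or 100 mg (6.1.2). Maximum participants: 34 + 3 = 37 (4.1).

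**Formulas.** Change = Table 3 dose − dose at onset. With the escalation bans applied, dose = min(dose at onset, Table 3 dose). Proposed dose = min(Table 3 dose, next lower Table 1 level).

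| Event | Dose at onset (mg) | Table 3 as written (mg) | Change (mg) | With bans applied (mg) | Proposed (mg) |
|---|---|---|---|---|---|
| First | 100 | 75 | −25 | 75 | 75 |
| First | 75 | 75 | 0 | 75 | 50 |
| First | 50 | 75 | +25, barred | 50 | 25, if approved |
| Second | 75 | 50 | −25 | 50 | 50 |
| Second | 50 | 50 | 0 | 50 | 25, if approved |

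Table 3 works as intended for 100 mg at a first event and 75 mg at a second. In the other three rows, once the bans are applied, the participant resumes at the dose on which the event occurred.

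**Can these states be reached?** Yes. A participant may enter on 75 or 50 mg, or be stepped down under Table 2 or 4. One route to the last row is 100 to 75 mg after a first QTcF event, then 75 to 50 mg under Table 2 or 4, then a second QTcF event.

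**Does another rule supply the reduction?**

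- Table 2's one-level step does not apply, because its title excludes QTc prolongation.
- The one-level rule in 6.6 follows a permissive sentence: for such toxicity, dosing may be delayed or reduced. It fixes the size of a step once a reduction is made; it does not require one.
- The escalation bans remove the increase from 50 to 75 mg but do not touch 75 to 75 or 50 to 50 mg.

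**Size.** At a first event on 75 mg, Table 3 against the next level down is 75/50 = 1.5. For a participant on 50 mg, with the bans applied, the comparison is 50/25 = 2.0, and only if the Sponsor approves 25 mg. Without approval no lower dose is available.

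Doses doubled for a moderate CYP3A4 inducer (6.5.1) are a separate case that Table 3 does not address. They are left out of the table above.

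**The case against.** A reader might infer that the protocol directs a dose increase, from 50 to 75 mg, after a Grade 3 QTcF event. The documents do not support that. Two sentences forbid escalation after a reduction, and 75 mg cannot be a reduced dose for someone on 50 mg. Read as a whole, the protocol contradicts itself here, and the sensible resolution is 50 mg. For the same reason, setting 75 mg against 25 mg (three times) is not a fair measure: the first dose is barred, and the second needs Sponsor approval.

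A reader might also infer that 75 to 75 mg breaks the one-level rule in 6.6. It does not, since that rule governs step size only. The firm conflict is with the word reduced in Table 3 and in the sentence that introduces it.

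The safeguards are substantial. Glasdegib is interrupted and restarts only after mQTcF has recovered to 480 msec or less, or to within 30 msec of baseline. Electrolytes and QT-prolonging drugs are corrected, ECGs follow at least weekly for two weeks, and a third event ends glasdegib. Every Grade 3 event is an SAE reported within 24 hours (8.3.1.1, 8.3.11), safety issues go to the sponsor at once (Section 8), and the investigator may stop glasdegib for any reason. These points stand and lower the severity. None of them states a lower resumption dose. The requirement to agree deviations with the Medical Monitor is not clearly triggered when a site follows Table 3 exactly.

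Finally, the amendment history says that the QTcF table was aligned with the US label at Amendment 5, so the fixed doses may be deliberate. The label is not among the documents, and the entry concerns an earlier version. Even if deliberate, fixed doses leave open what to do for participants whom this protocol starts at 50 or 75 mg.

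**Conclusion.** The point holds as a wording defect with a safety consequence. For participants lowered for a non-QTcF reason, Table 3 gives no reduction at a first event on 75 mg or a second event on 50 mg, contrary to its own description. At a first event on 50 mg it contradicts the escalation bans, and applying them again leaves the dose unchanged.

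The unconditional size is 75 against 50 mg at a first event on 75 mg. The conclusion assumes that sites follow Table 3 as written and that the dose at onset is a Table 1 dose not doubled for an inducer. The number affected is unknown. It requires glasdegib treatment, an earlier non-QTcF reduction and then a Grade 3 event, and the documents count none of these. The bounds are 0 to 37, and some of the 37 may receive azacitidine alone. With the safeguards in place and no analysis affected, this is a minor safety fix.

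**What to change.** Reword the two resume rows of Table 3: *Resume at 75 mg (first QTcF interruption) or 50 mg (second), or at the next lower Table 1 dose level if that is lower; never above the dose at onset.* Keep Table 1's Sponsor approval for any dose below 50 mg. State that the Medical Monitor agrees the action for participants on 25 mg, on 50 mg without that approval, or on a dose doubled for an inducer. Discontinuation after two earlier QTcF interruptions stays as it is.

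The main new effect is 75 to 50 mg at a first event; 50 to 25 mg applies only with approval. The change needs two table rows or an investigator letter, with no added visits or procedures. The downside is that a few participants may receive a lower dose or stop glasdegib earlier. If glasdegib stops, 6.6.1 already allows azacitidine alone where there is clinical benefit, after discussion with the sponsor.

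### Protocol Table 3 puts no ceiling on its baseline-relative resume limit, so at a baseline of 471 msec or more a held participant can meet the resume row while mQTcF is still in the Grade 3 range.

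*Protocol*

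**What the plan says.** All three rules stand in Table 3 of Protocol Section 6.6.1.

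- **Interruption.** Grade 3 is at or above "501 msec on at least 2 separate ECGs", and the action ticked for Grade 3 is "Interrupt treatment".
- **Resumption.** A held Grade 3 participant with no prior QTcF-related interruption, or with one, may resume at a reduced dose "when mQTcF interval returns to within 30 msec of baseline or" is at or below 480 msec. With two prior interruptions, glasdegib stops permanently.
- **Monitoring.** For Grades 2 to 4 the instruction is "Monitor ECGs at least weekly for 2 weeks following resolution of mQTcF prolongation" to 480 msec or less. This row has no baseline-relative alternative.

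Severity is graded on mQTcF, obtained by "calculating a mean QT of 3 consecutive ECGs performed approximately 2 minutes" apart, so the hold and resume rows use the same scale. At Grades 1 and 2 (450 to 500 msec) the action is "Continue treatment at same dose".

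Table 3 uses baseline in the resume row and in the Grade 4 definition but does not identify the ECG. Sections 5.1 and 5.2 set no QTc limit. The Schedule of Activities leaves ECGs to site standard of care. SAP Sections 5.3.4 and 6.3.4 mark ECG data as not applicable, so the SAP does not supply the definition either.

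**The concern.** A hold rule and a resume rule should not both apply to the same state. Here the hold is an absolute threshold, while one limb of the resume rule moves with the participant's own baseline and is not capped. At a high enough baseline the moving limit passes the fixed one. The monitoring row is also absolute, so it separates from the resume row at a lower baseline still.

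Section 6.6.1 makes Table 3 mandatory once QTcF exceeds 480 msec. Where its rows disagree, the decision to re-expose a participant, and the time at which the follow-up ECGs begin, depend on which row the site follows. The undefined baseline adds to this, because the resume limit moves one for one with whatever value is used.

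**Working it through.** The protocol gives no figure to reproduce. The check is one of threshold logic in whole milliseconds, as Table 3 is printed.

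**Inputs**
- Hold: mQTcF ≥ 501 (Table 3, Grade 3).
- Resume: mQTcF ≤ baseline + 30, or mQTcF ≤ 480 (Table 3, resume rows).
- Monitoring clock starts: mQTcF ≤ 480 (Table 3, monitoring row).
- Baseline *b*: not defined or capped in the documents. Assumption: values from 450 to 500 msec are examined.

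**Step 1: highest value that permits resumption.** The limbs are alternatives, so the limit is max(480, *b* + 30).

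**Step 2: overlap with the hold range.** Overlap needs *b* + 30 ≥ 501, that is *b* ≥ 471. If being within 30 msec is read strictly (difference of 29 or less), it needs *b* + 29 ≥ 501, that is *b* ≥ 472.

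**Step 3: separation from the monitoring row.** Resumption above 480 needs *b* + 30 > 480, that is *b* > 450. On the strict reading, *b* + 29 > 480 gives *b* > 451.

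| Baseline (msec) | Highest value allowing resumption | Values in both hold and resume ranges | Can resume above 480? |
|---|---|---|---|
| 450 | 480 | none | no |
| 460 | 490 | none | yes |
| 470 | 500 | none | yes |
| 471 | 501 | 501 | yes |
| 475 | 505 | 501–505 | yes |
| 480 | 510 | 501–510 | yes |
| 490 | 520 | 501–520 | yes |
| 500 | 530 | 501–530 | yes |

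Baselines of 471 to 480 are themselves Grade 1 on Table 3. The last two rows need a baseline that is already Grade 2.

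**Step 4: does the two-ECG condition remove the overlap?** No. Take a held participant with a baseline of 471 and three consecutive ECGs at 501. More than one ECG is at 501, so Grade 3 is met. The mean is 501 = 471 + 30, so the resume limit is met as well.

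**Step 5: alternative reading.** If both limbs had to hold, the limit would be min(480, *b* + 30), never above 480, and there would be no overlap at any baseline. The text joins the limbs with *or*.

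**The case against.** **Reachability.** Amendment 6 only continues people already enrolled, and Section 4.1 refers the design back to Amendment 5. The amendment log (Appendix 13) shows that Amendment 5 had a QTc exclusion, which may have made a baseline of 471 msec rare or impossible for most. This stands as a limit on size. It does not close the gap, because the threshold is not in the documents. The same log exempts pacemaker participants from that exclusion. It also records that they were exempt from the mQTcF dose rules, but the current Table 3 prints no such exemption.

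**Sequence.** The resume row follows the interruption and speaks of a return. A reader might infer that one ECG set can order the hold and lift it at the same moment, and the wording does not support that. The sequential reading leaves the overlap in place, however. With a baseline of 475, a participant held above 505 who falls into 501–505 has returned to within 30 msec and is still in the Grade 3 range.

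**On-drug baseline.** Section 6.1.2 states that "The starting dose regimen will be the same as the most recent regimen received" on the earlier study, so participants on glasdegib enter already exposed. A reader might infer that a Grade 2 ECG at entry becomes baseline, giving resume limits of 511 to 530 msec (481 + 30 to 500 + 30). Nothing says so: Section 6.1.2 concerns dose, and Amendment 6 schedules no baseline ECG. Those figures show only what an undefined term leaves open.

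**Monitoring.** It would be too strong to say that follow-up ECGs are lost. The two weeks begin when mQTcF later reaches 480 msec or less. Until then the electrolyte and concomitant-medication actions and routine ECGs in Section 6.6.1 still apply.

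**Safety data.** A reader might also infer that SAE counts are distorted. They are not. Section 8.3.11 makes every Grade 3 or 4 mQTcF case an SAE, and Appendix 6 does the same for QTcF above 500 msec. Neither uses the resume row.

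**Safeguards and intent.** Section 8 requires prompt discussion of safety issues with the sponsor, resumption is at a reduced dose, and the log says the Amendment 5 QTc table was aligned with the US label. These reduce the risk that a site acts on the overlap. They do not make the rows agree.

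**Conclusion.** The inconsistency is real and conditional. On the printed wording, the resume and Grade 3 ranges overlap for baselines of 471 msec or more (472 on the strict reading), and there is no overlap at 470 or below. The resume and monitoring rows part company for baselines above 450 msec, with the effect that the two-week monitoring is deferred.

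This rests on two readings: that the limbs are alternatives, as written, and that baseline is not otherwise capped, which the documents neither confirm nor exclude. The population is at most 34 + 3 = 37, fewer once those on azacitidine alone are removed. The number with such a baseline is not given and may be zero. The documents do not show that any participant has met the overlap.

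No endpoint definition or statistical figure changes. The point merits correction because Table 3 is a mandatory safety rule and should be capable of one reading.

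**What to change.** The sponsor should reconcile the Grade 3 interruption row, the resume rows and the ECG-monitoring row of Table 3 with each other, so that they can be applied together without contradiction at any baseline. It should also state which ECG is baseline for participants who enter Amendment 6 already on glasdegib. No threshold or monitoring rule is proposed here; the clinical content is for the sponsor's medical team.

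The cost is a wording change to one table and one definition, with the ethics approval that Appendix 1 requires for an amendment. The endpoint, analysis set and SAP summaries are unchanged. Whether the number of ECGs changes depends on how the sponsor resolves the rows.
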